An Open-label Study to Investigate the Efficacy and Tolerability of Aczone Gel, 7.5% in the Treatment of Acne Vulgaris in Men and Women With Skin of Color

[name]

NCT03681470

Document Date: Feb 7, 2022

Protocol Document for 17-01277
Principal Investigator: [name].
Mount Sinai

Brief Summary of Research

Acne vulgaris is a common skin disease characterized by inflammatory papules, pustules, and comedones that is prevalent in men and women of color. Research has demonstrated that Aczone[®] (dapson) gel, 7.5% used once daily is effective, safe, and well-tolerated for the treatment of acne in both men and women; however, no data is available regarding its efficacy and safety in skin of color (SOC). The current study aims to investigate the therapeutic impact of Aczone gel 7.5% in SOC males and females ages 18 and older with acne vulgaris. The study will also evaluate the impact of Aczone[®] gel on hyperpigmentation and PIH of the face.

Objectives

The purpose of this study is to evaluate the safety and efficacy of Aczone[®] gel, 7.5% administered once daily for 24 weeks in males or females with skin of color (SOC), defined as Fitzpatrick Skin Types IV, V, or VI, for the treatment of facial acne vulgaris.

Background

Acne vulgaris is a common skin disease characterized by inflammatory papules, pustules, and comedones that is prevalent in men and women of color. In fact, acne is the most common dermatologic diagnosis made in SOC populations (1). Although individuals of all skin types can develop acne vulgaris, there are important differences in darker skin types that are important to consider when choosing an optimal treatment (2).

From a diagnosis standpoint, acne in women of color is more likely to present on the cheek area, as opposed to a chin and cheek predominance in white women (2). Complications from acne are of great concern in this population, as women of color are more likely to develop keloids, hypertrophic scars, and post-inflammatory hyperpigmentation (PIH) as a result of acne lesions (3). PIH may last for weeks to months and, in many cases, is more troublesome to patients than the acne itself (2). Overall, facial acne and its sequelae have a greater impact on perception of appearance, negative emotions, and social functioning in women of color than white women (2).

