2. Change from baseline in Post Acne Hyperpigmentation Index (PAHPI) at weeks 12, 18, and 24.
3. Change from baseline in Melanin Index (MI) of target lesion at weeks 12, 18, and 24
4. Change from baseline in the proportion of subjects with score of 0 or 1 on ASIS “dark spot” score at weeks 4, 12, 18, and 24.
5. Proportion of subjects with GAAS of 0 (none) or 1 (minimal) at weeks 4, 12, 18, and 24

6. Percent change from baseline in all lesion counts (inflammatory, noninflammatory, and total) at weeks 4, 12, 18, and 24.

f) Procedures Involved in the Human Research

This is a single-center, single-group, open-label study using Aczone® (dapson) gel 7.5%. All subjects will receive the study medication. Aczone® gel is an off-white to yellow gel with suspended particles. It is supplied in an airless pump containing a polypropylene bottle with a high density polyethylene piston. It will be dispensed as a 60g pump.

Subject will apply Aczone® once daily to the entire face. Study drug must not be applied to other areas of the body, including the upper chest, upper back or shoulders.

Prior to the start of the study, potential subjects will be given an IRB-approved Informed Consent Document (ICD) containing a Health Insurance Portability and Accountability Act (HIPAA) disclosure agreement to read, understand, and sign. All questions about the study should be answered to the satisfaction of the candidate subject. They will have all of their study-related questions answered by the PI or designee, and if they agree to participate, the subject will sign two original copies of the ICD. The subjects will retain one original copy and one original copy will be kept in the study file. The subjects who sign an ICD will be assigned a screening number.

After providing informed consent, subjects will be assessed for study eligibility at the Screening visit (day -28 to day -1), which includes review of medical history and concomitant, acne lesion counting and severity ratings, and serum pregnancy test (if applicable). The PI or a medically qualified designee must review this information (i.e. medical history, concomitant medication, and eligibility review) for each subject to confirm their eligibility before enrollment. A total of 20 subjects who meet eligibility criteria will undergo Baseline / Day 0 assessments. Subjects will return for visits at weeks 4, 12, 18, and 24. There will be a phone visit at week 8.

Study Assessments and Efficacy Measures:

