Global Acne Assessment Score (GAAS):

The subject's acne severity will be assessed by the investigator using a 5-point GAAS at screening, baseline, and weeks 4, 12, 18, 24.

Grade	Description
0	None No evidence of facial acne vulgaris
1	Minimal Few noninflammatory lesions are present; a few inflammatory lesions (papules/pustules) may be present; no nodulo-cystic lesions present
2	Mild Several to many noninflammatory lesions are present; a few inflammatory lesions are present; no nodulo-cystic lesions present.
3	Moderate Many noninflammatory and inflammatory lesions are present; no nodulo-cystic lesions are present.
4	Severe Significant degree of inflammatory disease; papules and pustules are a predominant feature; a few nodulo-cystic lesions are present (no more than 2)

Lesion Counts:

The lesion counts, including inflammatory and non-inflammatory lesions, will be performed at screening, baseline, and weeks 4, 12, 18, and 24. Inflammatory lesions (papules, pustules, nodules/cysts) and

noninflammatory lesions (open comedone, closed comedone) will be counted individually. The sum of the inflammatory lesion counts and non-inflammatory lesion counts will be totaled.

ASIS ®:

Acne Symptom and Impact Scale (ASIS ®) will be given to subjects' for completion at baseline and weeks 4, 12, 18, and 24. The ASIS ® contains 9 items assessing symptom severity and 8 items assessing the psychosocial impact of acne vulgaris (6). High scores on the ASIS® indicate the presence of more severe symptoms, whereas higher scores on the ASIS indicate better outcomes on acne health-related quality of life.

PAPHI:

The postacne hyperpigmentation index (PAHPI) has been shown to be a reliable and valid score measuring post-inflammatory hyperpigmentation from acne (7). PAHPI will be scored using the following formula:

Total PAHPI = S + I + N

PAHPI Score can range from 6-22.

Lesion Size (S)

Weighted Score (S)	Median Lesion size
2	<3mm
4	3-6mm
6	7-10mm
8	>10mm

Lesion Intensity (I)

Weighted Score (I)	Median Lesion Intensity
3	Slightly darker than surrounding skin
6	Moderately darker than surrounding skin
9	Significantly darker than surrounding skin

Lesion Number (N)

Weighted Score (N)	Number of Lesions
1	1-15
2	16-30
3	31-45

4	46-60
---	-------

5	>60
---	-----

Melanin Index:

A narrowband reflectance spectrophotometer (mexameter MX-16) will be used to measure the degree of pigmentation of involved and adjacent uninvolved skin of one representative facial PIH lesion (8).

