The mexameter contains 16 light emitting diodes arranged circularly that emit light at wavelengths of 568nm (green), 660nm (red), and 880nm (near infrared). The machine then measures the amount of light absorbed and reflected by the skin to measure the melanin content (melanin index or “M” – red and near infrared light) and hemoglobin content (erythema index or “E” – green and right light).

One target lesion will be chosen by the investigator, which will be the darkest spot involved by post-inflammatory hyperpigmentation without evidence of active acne lesion (inflammatory or non-inflammatory lesion). The target lesion must be on the face and easily accessible with the mexameter probe. The probe will be applied to the target lesion on the skin with light, constant pressure. Both the “M” and “E” indices will be recorded. The location of the target site will be recorded using distance from anatomic landmarks.

Skin Phototype Assessment:

At screening, Fitzpatrick skin type (FST) will be rated by the investigator:

- I: always burns, never tans (very pale)
- II: always burns, tans minimally (pale)
- III: burns moderately, tans gradually (light brown)
- IV: burns minimally, always tans well (moderate brown)
- V: rarely burns, tans profusely (dark brown)
- VI: never burns, deeply pigmented (very dark brown)

Photography:

Standardized photographs will be taken by study personnel at baseline and weeks 12, 18, and 24 using standardized cameras and photographic equipment.

Subject Safety Measures:

The following safety measures will be collected:

- Adverse events
 - o The investigator will question the subject at all scheduled visits and one phone visit to determine whether adverse events were experienced since the prior visit. The adverse event and all applicable information (date of onset, date of stop, duration, outcome, severity, relationship to study drug, action or treatment required) will be obtained and recorded on the source documents and adverse event CRF.
- Local tolerability assessments

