- Skin phototype assessment (Fitzpatrick Skin Type)
- Lesion Counting
- Global Acne Assessment Score (GAAS)
- Adverse events
- Urine pregnancy

Baseline

- Inclusion/Exclusion
- Adverse events
- Concomitant medications and procedures
- Lesion Counting
- Melanin index

- GAAS
- Post Acne Hyperpigmentation Index (PAHPI)
- ASIS dark spot score
- Local tolerability assessment
- Photography
- Urine pregnancy
- Product dispensation/return

Week 4 –

- Adverse events
- Concomitant medications and procedures
- Lesion Count
- GAAS
- ASIS dark spot score
- Local tolerability assessment
- Pregnancy test
- Product dispensation/return

Week 8 Phone Visit –

- Adverse events
- Concomitant medications and procedures

Week 12 –

- Adverse events
- Concomitant medications and procedures
- Lesion Counting
- GAAS
- PAHPI
- ASIS dark spot score
- MI
- Photography
- Local tolerability assessment
- Product dispensation/return
- Urine pregnancy test

Week 18 –

- Adverse events
- Concomitant medications and procedures
- Lesion Counting
- GAAS
- PAHPI
- ASIS dark spot score
- MI
- Photography
- Local tolerability assessment
- Product dispensation/return
- Urine Pregnancy test

Week 24 –

- Adverse events
- Concomitant medications and procedures
- Lesion Counting
- GAAS
- PAHPI
- ASIS dark spot score
- MI
- Photography
- Local tolerability assessment
- Product return
- Urine Pregnancy test

Table 1: Assessment Schedule

Visit	1	2	3	4	5	6	7
Week	-4 to BL	0 (BL)	4	8 phone	12	18	24
Visit Window (days)			±3	±3	±3	±3	±3
Assessment							
Informed Consent	X						
Demographics	X						
Inclusion/Exclusion	X	X					
Medical History	X						
Fitzpatrick Skin Type	X						
AE/SAE assessment	X	X	X	X	X	X	X
Concomitant medications	X	X	X	X	X	X	X
Concomitant procedures	X	X	X	X	X	X	X
Photography		X			X	X	X
Urine Pregnancy Test	X	X	X		X	X	X
Lesion Count	X	X	X		X	X	X
GAAS	X	X	X		X	X	X
ASIS ®		X	X		X	X	X
PAHPI		X			X	X	X
Mexameter – Melanin Index		X			X	X	X
Local tolerability		X	X		X	X	X
Study Drug Dispensation and Return		X	X		X	X	X

g) Specimen Banking

Not applicable.

h) Data Management and Confidentiality

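### Target-lesion melanin index follows one fixed dark spot with no control, yet the SAP reads movement from baseline as a treatment effect, so natural fading of PIH would be credited to the drug

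*Combined protocol and SAP*

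**What the plan says.** Section f, Melanin Index, describes the target in two ways. It opens by measuring the "degree of pigmentation of involved and adjacent uninvolved skin of one representative facial PIH lesion". It then says that the investigator chooses one target, "which will be the darkest spot involved by post-inflammatory hyperpigmentation without evidence of active acne lesion", and records its position from anatomic landmarks, so the same spot is followed throughout.

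Secondary endpoint 3 in section e is "Change from baseline in Melanin Index (MI) of target lesion at weeks 12, 18, and 24". The "Mexameter – Melanin Index" row of Table 1 agrees with the visit lists: baseline and weeks 12, 18 and 24, with no reading at screening. The documents do not name the visit at which the target is picked. Baseline is the natural inference, because MI, PAHPI and photography all start there.

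Section f also states: "This is a single-center, single-group, open-label study", and "Subject will apply Aczone® once daily to the entire face". On natural course, the Background says: "PIH may last for weeks to months".

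Section k, Analysis of secondary Endpoints, lists MI among the outcomes shown in baseline-by-visit frequency tables and counts many off-diagonal subjects as evidence for a treatment effect. It then applies a two-sided paired t-test to the change from baseline, with Bonferroni correction over an unstated number of tests and a Wilcoxon signed rank test in parallel.

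**The concern.** The endpoint follows a single existing spot, dark at the outset and free of active acne, for 12 to 24 weeks. That is the timescale on which the protocol itself says PIH lasts. Because the spot is fixed, new spots forming elsewhere on the face cannot offset its fading. With no control group and no untreated facial skin, the mean change in MI is natural course plus drug effect, and the data cannot split the two.

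Many single-group studies share this limit and simply describe change. Here the SAP states an inference rule that goes further. The Background gives evaluating the gel's impact on PIH as an aim, and section k reads movement from baseline as a treatment effect. A positive hyperpigmentation finding could therefore be reported when only ordinary resolution has occurred.

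**Working it through.** **The plan's own figure.** The only design calculation concerns GAAS: n = 20, a change of 1 grade, SD 0.513, two-sided 5%. With d = 1/0.513 = 1.95, exact paired-t power exceeds 0.999. If 0.513 is instead a per-visit SD with zero correlation, the SD of the change is 0.513 × √2 = 0.725 and power is 0.9999. The stated power above 90% is reproduced. It says nothing about MI, for which the documents give no mean, SD, lesion age or fading rate.

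**Natural fading with zero drug effect.** Let f be the mean untreated fall divided by the SD of the change. The paired t statistic then follows a noncentral t distribution with 19 degrees of freedom and noncentrality f × √20. The chance of a significant fall is the probability of exceeding the two-sided critical value. All values of f are assumptions.

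| f | noncentrality | 5% | 5%/3 | 5%/17 | 5%/29 |
|---|---|---|---|---|---|
| 0.25 | 1.12 | 18% | 9% | 2% | 2% |
| 0.5 | 2.24 | 56% | 37% | 16% | 12% |
| 0.75 | 3.35 | 89% | 76% | 50% | 42% |
| 1.0 | 4.47 | 99% | 96% | 83% | 78% |

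The divisors are possible readings of the Bonferroni family, which the SAP does not define:
- 3 is the MI visits alone.
- 17 is the secondary tests without lesion counts: GAAS change 3 + PAHPI 3 + MI 3 + ASIS 4 + GAAS 0 or 1 at 4 visits.
- 29 adds three lesion counts at four visits (17 + 12).

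Bonferroni lowers these probabilities but does not correct a mean that is shifted for reasons other than the drug.

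**Timescale of fading.** Suppose the spot's excess pigment fades exponentially with half-life h, so that 0.5^(t/h) remains. For assumed half-lives of 4, 8, 12 and 26 weeks, the untreated remainder is 13%, 35%, 50% and 73% at week 12, and 2%, 13%, 25% and 53% at week 24. The documents supply none of these half-lives. The range only shows what weeks to months could mean over this follow-up.

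**Selection of the darkest spot.** This sets fading and drug effect to zero. Take 10 spots and a repeat-reading correlation of 0.8; the expected maximum of 10 standard normal values is 1.54.
- If the mexameter reading itself picked the spot, the expected fall would be (1 − 0.8) × 1.54 = 0.31 SD of a single reading, significant in about 57% of simulated trials.
- If the spot is picked by eye, with error independent of the device, the expected fall is 0 and significant falls occur at the nominal one-direction rate of 2.5%.
- If half of the unstable variance is real transient darkness that both eye and device register, the fall is 0.5 × 0.2 × 1.54 = 0.15 SD, significant in about 18% of trials (2% at 5%/17).

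The protocol has the investigator choose the spot and then apply the probe. The first case is therefore an upper bound, and selection is a secondary contributor.

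**The case against.** The strongest reply is that the size of the problem is unknown. The Background gives a loose duration and no rate, and the darkest spot may be the most persistent one. That is correct. The percentages are conditional on assumed fades and do not predict this trial.

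A second reply is that MI is secondary in an openly uncontrolled study of 20 subjects, so readers will discount it. That would be enough if the SAP only described change, but it states a treatment-effect reading.

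A third is that adjacent uninvolved skin is also measured. Subtracting it would remove general skin-tone change but not loss of the spot's own excess pigment. In any case, neither the endpoint nor the SAP uses the adjacent reading.

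Some stronger readings are tempting but not supported:
- A reader might infer that picking the darkest spot alone yields a false finding in more than half of trials. That needs selection by the device reading, which the protocol does not describe. The lesion is also called representative elsewhere in the same section.
- A reader might blame the 12-week wait for the first re-reading. An earlier reading would show the course of fading but would not separate it from drug effect.
- A reader might take the screening period as four weeks of untreated observation. It runs from day -28 to day -1, and exclusion 6a bars listed topical products only within 2 weeks of baseline, so it may be one day long or overlap washout.

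**Conclusion.** The point holds for interpretation of the MI endpoint. The design cannot distinguish natural lightening of a fixed PIH spot from a drug effect, and the SAP's stated reading would credit the drug with both. With no drug effect, the chance of a significant fall runs from about 18% to 99% at 5% for fades of 0.25 to 1 SD of the change, and from 2% to 83% over 17 tests. This rests on an assumed fade, an assumed test count, 20 completers and baseline as the selection visit.

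It does not follow that the gel has no effect on PIH, or that an observed fall would be spurious; the trial simply could not tell. PAHPI is not a way out, because it has the same lack of a control.

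**What to change.** 1. In section k, replace the treatment-effect reading for MI and PAHPI with change over time. State that a fall from baseline alone does not support a drug effect on PIH.
2. Choose and map the target lesion at screening, take one MI reading there, and use a separate Visit 2 reading as baseline. State in advance how to handle a spot that has active acne by Visit 2. This deals with selection, not with fading.
3. Report the screening-to-baseline MI change descriptively only, noting that the interval varies from 1 to 28 days and may overlap the 2-week topical washout.
4. Reconcile the representative and darkest descriptions of the target, and name the visit at which it is chosen.

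The cost is a few minutes at an existing visit for up to 40 screened subjects, some wording, and a more cautious PIH claim. For subjects already past screening, item 2 and the item 3 report are no longer available. The wording in item 1 still is, and it matters most.

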5. Accumulated safety and data information will be reviewed annually.
6. N/A
7. N/A

8. Adverse events will be graded using the Common Terminology Criteria for Adverse Events (CTCAE).
9. The study will be conducted in compliance with regulatory requirements and Good Clinical Practice. Quality control will be applied to each stage of data handling to ensure that data are accurate, reliable and processed correctly.
10. Should a temporary or permanent suspension of our study occur, the occurrence will be reported to the PPHS, sponsor, and IRB.

Part II. Data Monitoring Committee/Data Safety Monitoring Board (DMC/DSMB)

Not applicable

j) Withdrawal of Subjects

When an individual who has signed the ICF is not enrolled in the study or withdraws/is withdrawn prior to completing the study, the reason is to be documented on the Discontinuation/Completion Form (or equivalent) and in the final study report. Reasons for subject withdrawal may include:

- Not enrolled (e.g. fails to meet inclusion/exclusion criteria, chooses not to enroll, etc.)
- Participant is determined to be ineligible after enrollment
- Subject's choice to withdraw
- Investigator terminated (e.g. noncompliance, etc.)
- Adverse Event
- Pregnancy
- Lost to follow-up
- Other

Subjects may withdraw from the trial at any time at their request, or they may be withdrawn at any time at the discretion of the Sponsor, PI, or designee for safety, behavioral, or administrative reasons. Subjects may be withdrawn from this study without their consent if the research study is being stopped; or if the instructions of the study team have not been followed.

If a subject does not return for a scheduled visit, *three documented attempts will be made to contact the subject in order to establish the reason for withdrawal, and* the outcome will be documented. The PI or designee should inquire about the reason for withdrawal, request that the subject return for a final visit, if applicable, and follow-up with the subject regarding any unresolved adverse events.

Should a subject withdraw from the trial and also withdraw consent for disclosure of future information, no further evaluations should be performed and no additional data should be collected. The PI and staff may retain and continue to use any data collected before such withdrawal of consent. Removed or withdrawn subjects will not be replaced.

If a subject fails to report to the test facility for a scheduled visit and cannot be rescheduled within the permitted window of time (as applicable), the Site should consult with the Sponsor to determine if the subject should be documented as having withdrawn/dropped from the study.

Risks to Subjects

The following list of side effects is the ones that may be associated with the use of dapsone gel:

Common:

- Application site reactions:
 - Dryness
 - Peeling
 - Oiliness
 - Erythema
 - Pruritus
- Temporary yellow or orange discoloration of treated skin and local facial hair (when used in conjunction with benzoyl peroxide)

Rare:

- Methemoglobinemia – Cases of methemoglobinemia have been reported post-marketing in subjects using dapsone 5% gel twice daily. Initial signs and symptoms include slate grey cyanosis, which may be observed on the buccal mucous membranes, lips, and nail beds. Increased susceptibility to methemoglobinemia is seen patients with glucose-6-phosphate (G6PD) deficiency. The risk is also elevated in individuals taking other medications that induce the formation of methemoglobin (i.e. sulfonamides, acetaminophen, acetanilide, aniline dyes, benzocaine, chloroquine, naphthalene, nitrates and nitrites, nitrofurantoin, nitroglycerin, nitroprusside, pamaquine, para-aminosalicylic acid, phenacetin, phenobarbital, phenytoin, primaquine, quinine). Dapsone gel should be avoided in patients with known history of congenital or idiopathic methemoglobinemia. Patients should be instructed to discontinue use of dapsone gel immediately and seek medical attention if they develop any signs of cyanosis.
- Hemolysis – The use of oral dapsone has been associated with the development of hemolysis and hemolytic anemia, particularly in patients with G6PD deficiency. G6PD deficiency is most common in individuals of Mediterranean, African, South Asian, and Middle Eastern descent. Studies and post-marketing on dapsone gel has not demonstrated any clinically relevant hemolysis or hemolytic anemia in treated subjects. Lab changes suggestive of hemolysis have been seen in patients with G6PD deficiency using dapsone gel 5%. Dapsone gel should be used with caution in patients taking oral medications known to increase serum levels of dapsone, including trimethoprim/sulfamethoxazole, and should be avoided in patients taking oral dapsone and anti-malarial medications due to risk of hemolytic reactions.

- Peripheral neuropathy – peripheral neuropathy has been observed with use of oral dapsone. No cases have been reported in patients using dapsone gel.
- Significant skin reactions (toxic epidermal necrolysis, erythema multiforme, morbilliform and scarlatiniform reactions, bullous and exfoliative dermatitis, erythema nodosum, urticarial) – With the exception of urticaria, no significant skin reactions have been observed during clinical trials and post-marketing with use of dapsone gel.

Aczone gel is designated as pregnancy category C, meaning that there are no adequate and well controlled studies in pregnant women. Dapsone administered orally in rats and rabbits has demonstrated embryocidal effects during the period of organogenesis when dosed at 425 to 1400 times the maximum recommended human dose (MRHD).

Pregnancies and suspected pregnancies (including a positive pregnancy test regardless of age or disease state) of a female subject or the female partner of a male subject occurring while the subject is on study drug, or within 30 days of the subject's last dose of study drug, are considered immediately reportable events. Study drug is to be discontinued immediately and the subject instructed to return any unused portion of the study drug to the investigator(s). The pregnancy, suspected pregnancy, or positive pregnancy test must be reported to Allergan Safety immediately facsimile using the Pregnancy Report form provided by the company. The female should be referred to an obstetrician-gynecologist experienced in reproductive toxicity for further evaluation and counseling. The Investigator(s) will follow the female subject until completion of the pregnancy, and must notify Allergan Safety of the outcome of the pregnancy as a follow-up on the follow up Pregnancy Reporting form.

Provisions for Research Related Harm/Injury

If a subject experiences a research injury, Mount Sinai West will provide or arrange for medical treatment at no cost. If the subject chooses to see their own personal doctor we will not offer to pay for the expenses. A research injury is any physical injury or illness caused by participation in the study. If a subject is injured by a medical treatment or procedure that would have been received even if the subject weren't in the study; that is not a research injury. Payment for things such as lost wages, expenses other than medical care, or pain and suffering is not offered. To help avoid injury, it is very important to follow all study directions.

Please be aware that some insurance plans may not pay for research-related injuries. Subjects should contact their insurance company for more information.

Unreimbursed medical expenses not covered by insurance or other third party coverage will be reimbursed by the sponsor for medical treatment for any injury that, in the opinion of the study doctor and the sponsor, is directly caused by the study drug/investigational product or by procedures required by the study protocol which would not have been performed as part of regular medical care.

Provisions to Protect the Privacy Interests of Subjects

Only subjects who have given us permission to contact them for studies will be contacted. All conversations with subjects and potential subjects will be conducted in a private examination room with the subject. Subjects' privacy will be protected by performing any study-related procedures in a private examination room. Family members will be allowed to remain in the room only if the subject allows this. No information regarding the subject's disease, treatment or the fact that he/she is involved in a study will be conveyed. Subjects will be made to feel at ease, by allowing them sufficient time to discuss the study and any potential queries.

All parties will ensure protection of subject personal data and will not include subject names on any Sponsor forms, reports, publications, or in any other disclosures. In case of data transfer, Sponsor will maintain high standards of confidentiality and protection of subject personal data.

The ICF (containing the HIPAA disclosure agreement) must be agreed to by Sponsor and the IRB and be in compliance and consistent with ICH GCP, local regulatory requirements, and legal requirements.

The investigator must ensure that each study subject is fully informed about the nature and objectives of the trial, possible risks associated with participation. The investigator, or a trained person designated by the investigator, will obtain written informed consent on two copies from each subject before any trial-specific activity is performed. The subject will retain one copy, and one will be kept in the study file. The ICF used in this trial, and any changes made during the course of the trial, must be prospectively approved by both the IRB and Sponsor before use.

Economic Impact on Subjects

Allergan, the manufacturer of the study drug, will provide the study drug. Allergan also covers the cost of all study-related tests and procedures. While in the study, the subject will still need to get regular medical care. The subject will still have to pay for the costs of regular medical care that is not a part of this study.

Taking part in this research study may lead to added costs to the subject. If the laboratory tests or physical examinations reveal information about his/her health, additional tests, treatments and doctors appointments may be required which could present additional costs to him/her or his/her insurance company.

Payments to Subjects

Subjects will be compensated \$25.00 per completed in-person visit for a total of \$150.00 upon completion of the study. Subjects will not be compensated for the week 8 phone visit. Subjects who complete only the screening visit will not be eligible for compensation. If the subject withdraws or is withdrawn before completing the study, he/she will receive an amount of money for the visits which have been completed. They will not have to submit receipts to receive this reimbursement. This payment will come in the form of a check at the end of the subject's participation in the study.

Consent Process

We will be obtaining written consent as a part of this study. No subject will be evaluated without a signed Informed Consent Form (ICF).

The consent process will take place in a private exam room where the subject will have ample time to review and read the consent form. Subjects will be given time to ask questions and may take additional time to consider their options. Subjects will be informed that they do not have to participate and may withdraw consent at any time.

After understanding and agreeing, the subject will express their consent to participate in the study by signing an original copy of the ICF. The subject will receive a copy of their signed document for their records.

We will follow the SOP HRP-090 Informed Consent Process for Research.

Process to Document Consent in Writing

We will be using the standard IRB Informed Consent template. The ICF must be agreed to by the Sponsor and the IRB and must be in compliance with ICH GCP, local regulatory requirements, and legal requirements.

The consent process and date that the consent is signed is documented in our source notes.

Study personnel will adhere to “SOP HRP-091 Written Documentation of Consent”.

Vulnerable Populations

This project will not include any vulnerable population subjects.

Multi-Site Human Research (Coordinating Center)

This project is a single site study.

Community-Based Participatory Research

This project will not involve any community-based participation.

Sharing of Results with Subjects

At the completion of the study, subjects will have the right to access their protected health information that is created during this research study that relates to their treatment or to payment,

provided such information is not exempted under certain laws and regulations. To request this information, subjects should contact the study doctor at the address listed above.

Subject to certain exceptions prescribed by law, subjects have a right to request access to the health information that we hold about and to request changes if the health information is incorrect or incomplete. Any request for access or corrections should be made to the principal doctor conducting this study.

Once all data and results are finalized, a summary will be made available to subjects.

External IRB Review History

This project is not using an external IRB.

Control of Drugs, Biologics, or Devices

Study drug is stored in a combination-locked room accessible only by clinical trials personnel. All study materials should be stored at room temperature (59°-77°F), and the Site is responsible for maintaining temperature logs. All study products received and dispensed will be inventoried and accounted for throughout the study. The investigator must maintain adequate records documenting the receipt, use, loss, or other disposition of the products on the Product Accountability Log. The log must identify the investigational product and account for its disposition by subject, including specific dates and quantities dispensed and returned. The log must be signed by the individual who dispensed/retrieved the study product and copies must be provided to the sponsor for inclusion in the Trial Master File.

At the completion of the study, all units of product dispensed (whether empty or containing unused product) must be collected by the Site and returned, along with un-dispensed product, to the Sponsor. Any container not returned by the Site must be accounted for in writing.

k) Statistical Analysis Plan

The adverse events will be tabulated according to their date of onset, duration, severity and relationship to the treatment. We will build Clopper-Pearson 90% confidence intervals for the proportion of adverse events considering their aggregation and stratification (e.g., by severity).

Sample Size Considerations

A sample size of $n=20$ subjects allows $>90\%$ power at 5% significance level for a two-sided paired t-test to detect at week 12 a minimum change in GAAS from baseline of 1 grade point. This calculation was performed in G*Power and it assumes a mean GAAS of 3.5 at baseline and a maximal standard deviation of 0.513.

Analysis of primary Endpoint

The primary analysis will apply a two-sided paired t-test to assess the significance of the change in GAAS from baseline to week 12. However, GAAS is an ordinal measurement and, for this reason, we will also apply a Generalized Linear Mixed-effects Model (GLMM) to assess the significance of the changes in GAAS after including potential covariates.

Analysis of secondary Endpoints

At each time point, the changes from baseline in ordinal secondary endpoints GAAS, PAHPI, MI, the proportion of subjects with a score of 0 or 1 on ASIS “dark spot,” the proportion of subjects with $GAAS < 2$ will be presented in frequency tables. The (i,j) entries in the tables are counts of subjects in category i at baseline that moved to category j at that time point. A high frequency of counts falling off the main diagonal of the table is evidence in favor of a significant treatment effect. Similarly, to the primary endpoint, we will apply a two-sided paired t-test to assess the significance of changes from baseline in each outcome. We will apply the Bonferroni correction to adjust for the multiplicity of tests. In parallel, we will test pre vs. post differences in these ordinal outcomes with the Wilcoxon Signed Rank test. Discrepancies between the parametric and non-parametric approaches will be discussed on a case basis. In addition to this approach, we will fit an ordinal logit model, including all available time points, age, and gender as covariates.

The changes from baseline in lesion counts (inflammatory, non-inflammatory, and their aggregation) will be assessed with the two-sided paired t-test followed by Bonferroni correction. A Generalized Linear Mixed Model (GLMM) will be fitted to model the count of lesions as the dependent variable, time and inflammation as fixed effects, age, and gender as covariates. In this framework, we will include random intercept and slope for each subject’s trajectory. The contrasts will reveal differences between time points and treatment effect in inflammatory vs. non-inflammatory lesions.

Missing Data and Outliers

Missing data in the longitudinal data analysis will be handled by the mixed-effects approach which performs an appropriate adjustment of the coefficients’ degrees of freedom for each fitted model. We do not foresee issues with outliers due to the endpoints’ measurement level, most of them being ordinal.

Reference:

